5.1.3 Excluded therapies and medications, previous and concomitant

- Concurrent anti-cancer therapy (chemotherapy, radiation therapy, surgery, immunotherapy, biologic therapy, or tumor embolization) other than sorafenib.
- Concurrent use of another investigational drug or device therapy (i.e., outside of study treatment) during, or within 4 weeks of trial entry (signing of the informed consent form).
- Therapeutic anticoagulation with Vitamin-K antagonists (e.g., warfarin) or with heparins and heparinoids.
 - However, prophylactic anticoagulation as described below is allowed:

- Low dose warfarin (1 mg orally, once daily) with PT-INR $\leq 1.5 \times$ ULN is permitted. Infrequent bleeding or elevations in PT-INR have been reported in some subjects taking warfarin while on sorafenib or capecitabine therapy. Therefore, subjects taking concomitant warfarin should be monitored regularly for changes in PT, PT-INR or clinical bleeding episodes.
- Low dose aspirin (≤ 100 mg daily).
- Prophylactic doses of heparin.

5.2 Withdrawal of subjects from study

Subjects **must be withdrawn from the trial** (treatment and procedures) for the following reasons:

- Subject withdraws consent from study treatment and study procedures. A subject must be removed from the trial at his/her own request or at the request of his/her legally acceptable representative. At any time during the trial and without giving reasons, a subject may decline to participate further. The subject will not suffer any disadvantage as a result.
- Subject is lost to follow-up.
- Death.

Subjects **may be** withdrawn from the study for the following reasons:

- The subject is non-compliant with study drug, trial procedures, or both; including the use of anti-cancer therapy not prescribed by the study protocol.
- Pregnancy. Pregnancy will be reported as an SAE. (Note: subjects who have been withdrawn from treatment with study drug because of pregnancy should not undergo CT scans [with contrast]/MRI or bone scans while pregnant.)
- If, in the investigator's opinion, continuation of the trial would be harmful to the subject's well-being.
- Severe allergic reaction to sorafenib (such as exfoliative erythroderma or Grade 3 or 4 hypersensitivity reaction).
- The development of a second cancer.
- Development of an intercurrent illness or situation which would, in the judgment of the investigator, significantly affect assessments of clinical status and trial endpoints.
- Deterioration of ECOG performance status to 4.
- Use of illicit drugs or other substances that may, in the opinion of the investigator, have a reasonable chance of contributing to toxicity or otherwise skewing trial result.

Any subject removed from the trial will remain under medical supervision until discharge or transfer is medically acceptable.

In all cases, the reason for withdrawal must be recorded in the CRF and in the subject's medical records.

Details for the premature termination of the study as a whole (or components thereof [e.g. centers, treatment arms, dose steps]) are provided in Section 10 (Premature termination of the study).Screen Failures/Dropouts

A subject who discontinues study participation prematurely for any reason is defined as a “dropout” if the subject has already assigned to treatment/run-in/wash-out; administered at least one dose of study drug.

A subject who discontinues study participation for reasons other than toxicity after receiving sorafenib but not the Y-90 procedure is inevaluable and will be replaced. Subjects who are discontinued from the study early due to toxicities will be counted in the toxicity assessment.

A subject who, for any reason (e.g. failure to satisfy the selection criteria), terminates the study before the time point used for the definition of “dropout” (see above) is regarded a “screening failure”. Replacement

No withdrawn subjects will be replaced.

6. Treatment[s]

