6.3 TheraSphere

TheraSphere treatment is performed in the outpatient setting. Prior to initial treatment, a Technetium-99 Macroaggregated Albumin (Tc-99m MAA) scan will be performed using standard institutional practices. If there is an uncorrectable risk of flow to the gastrointestinal organs or risk of excessive shunting to the lungs, TheraSphere treatment will not be administered and the patient will receive alternative or no treatment as previously defined in the treatment plan

Following treatment, patients will remain at the hospital under medical observation until the physician determines that they can safely be discharged to home (usually 2-6 hours). All patients will be evaluated post-treatment to assess clinical experience and adverse experiences.

Patients will have 1-2 outpatient visits for pre-treatment evaluation to determine initial eligibility to receive TheraSphere, followed by a treatment visit for outpatient delivery of TheraSphere,.

Catheters will be placed in the hepatic artery in the angiography suites. No scheduled hospitalizations will be required, unless the physician determines that the patient should be admitted following treatment for management of a complication or adverse experience.

Pre-Therasphere Evaluation

Pre-treatment evaluation will include the initial screening by history, physical examination, laboratory and diagnostic studies (hepatic angiography and Tc-MAA Scan). A treatment plan will be developed, dosage will be calculated, and the initial TheraSphere activity vial will be ordered from the manufacturer (Nordion).

Diagnostic Imaging Studies

Contrast enhanced Computed Tomography Scanning of the Abdomen/Liver or Magnetic Resonance Imaging of the Abdomen/Liver

Technetium-99 Macroaggregated Albumin (Tc-99m MAA) Scan.

CT or MR scanning of the liver will be performed and the images used to calculate the appropriate liver volume for TheraSphere dose determination. Reasonable attempts will be made to use the same imaging modality as that used for pre-treatment for all subsequent evaluations of the patient related to dose determination.

The dose is calculated as described below (Section 7.3.3.4), using the appropriate reference liver volume and mass. Dosimetric techniques for TheraSphere are discussed in detail in the peer-reviewed literature.

The imaging scan is used to document the location and size of the hepatic lesion(s) and vascular anatomy where possible.

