^e CT will be the radiographic study of choice for baseline (CT of the chest is included at baseline) and re-staging evaluations (CT of the chest may be included if needed in re-staging); MRI may be substituted at any time in the course of the study as clinically warranted (eg iodine dye intolerance, elevated creatinine, tumor not clearly depicted on CT)

^f Treatment may continue after Course 2, including the same study assessment schedule, until one of the criteria for treatment discontinuation applies.

^g Patients who have an ongoing Grade ≥ 3 or serious adverse event that is at least possibly related to treatment will be contacted by the investigator or designee every week until the event is resolved or determined to be irreversible.

^h Every 3 months after discontinuation of treatment

ⁱ Hepatitis profile to include the following tests: hepatitis B virus surface antigen (HBSAG), hepatitis B virus core antibody (HBCAB), and hepatitis C virus antibody (HCVAB).

^j Samples Collection: Blood samples will be collected at the time of patients' scheduled visits as follows:Procedure for samples collection:

GI Medical oncology Research Staff will inform blood draw station to collect an extra set of blood sample (3 ml purple top tube with EDTA) for the purpose of the study, on the day of the patient's initial visit and per scheduled samples collection per protocol. at the GI Medical Oncology clinic visits. Collection times will correspond to those at which subjects are already having blood drawn for other purposes. Maximum blood draws would be 6 total(1) Screening; (2) Cycle 1/Day 1; (3) Cycle 2/Day 1; (4) Cycle 3/Day 1; (5) Pre-Yttrium-90, on the same day; and (6) End of Treatment. Once blood is collected, GI Medical Oncology research personnel will pick it up and deliver it to the laboratory of [name] and [name] for processing in batch and storage in freezer in -80 F. Processing will involve isolating plasma samples. **Cycle 1/Day 1** sample will be collected only if **Screening** sample was collected more than 7 days prior. **Pre-Yttrium-90** sample will be collected only if **Cycle 2/day 1** sample was collected more than 7 days prior. And vice versa, **Cycle 2/Day 1** sample will be collected if **Pre-Yttrium-90** sample was collected more than 7 days prior.

Samples will each be labeled according to the sample label listed below.

Sample label or per Z code labeling

Protocol #	sample
Subject Accession # -	
Date/Time prepared -	

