7.4.2 Pregnancies

The investigator must report to Bayer any pregnancy occurring in a study subject, or in his partner, during the subject's participation in this study. The report should be submitted within the same timelines as an SAE, although a pregnancy per se is not considered an SAE.

For a study subject, the outcome of the pregnancy should be followed up carefully, and any abnormal outcome of the mother or the child should be reported.

For the pregnancy of a study subject's partner, all efforts should be made to obtain similar information on course and outcome, subject to the partner's consent.

For all reports, the forms provided are to be used.

Progressive disease

If progressive disease leads to signs and symptoms that meet the criteria for an SAE (i.e., hospitalization, disability, death, or important medical event), the signs and symptoms should be reported as an SAE and not the underlying progressive disease.

Death

If any subject dies during the trial or within 30 days of the end-of-treatment visit, the investigator will inform Bayer and record the cause of death in detail (using the SAE Form) within 24 hours.

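### Section 5.2 lets failing patients be withdrawn from the study without saying that scans or survival follow-up continue, so PFS can be censored informatively in favour of the combination

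*Combined protocol and SAP*

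**What the plan says.** Section 5.2 has two lists. The mandatory one (withdrawn consent, loss to follow-up, death) describes withdrawal from the trial as covering both treatment and procedures. The discretionary one gives reasons for which subjects may be "withdrawn from the study for the following reasons". They include:

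- "The subject is non-compliant with study drug, trial procedures, or both; including the use of anti-cancer therapy not prescribed by the study protocol"
- "Deterioration of ECOG performance status to 4"
- "Development of an intercurrent illness or situation which would, in the judgment of the investigator, significantly affect assessments of clinical status and trial endpoints"

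On what happens next, the section says only: "Any subject removed from the trial will remain under medical supervision until discharge or transfer is medically acceptable". It names no scan and no survival contact.

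Table 7 has a survival row under post-treatment follow-up, timed by footnote h as "Every 3 months after discontinuation of treatment". It also schedules a CT/MRI tumour assessment at End of Treatment. The paragraph on deaths that follows Section 7.4.2 requires a report to the drug manufacturer "If any subject dies during the trial or within 30 days of the end-of-treatment visit".

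Section 8.1 makes PFS the primary objective, counted from start of therapy to progression or death. It estimates the median by a Bayesian event-time model and by Kaplan-Meier, and compares it with 4.1 months for sorafenib alone. It gives no rule for censoring, for new anticancer therapy or for withdrawal.

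**The concern.** Kaplan-Meier and the event-time model both treat a censored patient as having the same future risk as those still followed. The discretionary reasons tend to pick out patients for whom that is untrue. The argument is strong for ECOG 4, plausible for off-protocol anticancer therapy, and weaker for intercurrent illness.

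If such a patient has no documented progression and follow-up ends at withdrawal, the follow-up time counts but the event does not. The estimated median then rises. The trial has one arm and a historical comparator, so no concurrent control shares the bias. The investigator decides on withdrawal in an uncontrolled study. The same lost events feed the futility rule, which would stop an inferior combination less often.

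**Working it through.** **Inputs (Section 8.1).** Prior for the sorafenib median mS: IG(11, 41). Prior for the combination median mE: IG(2.17, 4.8). Stop if Pr(mE > mS | data) < 0.15. Looks start at 20 enrolled; maximum 40 patients; accrual 1.5 per month; 12 months of further follow-up.

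**Model.** With exponential event times, d events and total follow-up T, the posterior is mE ~ IG(2.17 + d, 4.8 + ln2 × T). Pr(mE > mS) then follows exactly from an F distribution.

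**Reproducing Table 8.** 5,000 simulated trials were run with Poisson accrual, a look at each new patient from 20 onward, and a last look 12 months after the 40th patient.

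| True median (months) | Table 8 Pr(stop) | Reproduced | Table 8 mean N | Reproduced |
|---|---|---|---|---|
| 2 | 0.993 | 0.993 | 21 | 21.0 |
| 3 | 0.529 | 0.528 | 31.4 | 31.4 |
| 4 | 0.100 | 0.103 | 38.3 | 38.2 |
| 5 | 0.017 | 0.018 | 39.7 | 39.7 |

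The model therefore matches the plan's own.

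**Effect of lost events.** Assumption: a share q of patients is censored at the moment the event would have occurred. The documents give no value for q. Of 40 patients, q = 5, 10 and 20% means 2, 4 and 8 people. Follow-up is unchanged and events fall to (1 − q)d, so the exponential median is multiplied by 1/(1 − q):

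- q = 5%: 4.1/0.95 = 4.3 months
- q = 10%: 4.1/0.90 = 4.6 months
- q = 20%: 4.1/0.80 = 5.1 months

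**Effect on the futility rule** (same simulation, Pr(stop)):

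| q | True median 2 | True median 3 | True median 4 |
|---|---|---|---|
| 0 | 0.993 | 0.528 | 0.103 |
| 5% | 0.978 | 0.420 | 0.075 |
| 10% | 0.947 | 0.326 | 0.051 |
| 20% | 0.824 | 0.171 | 0.020 |

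**Effect on the final posterior probability.** Take the plan's illustration of 25 events at a median of 4.1, so ln2 × T = 25 × 4.1 = 102.5, and replace d by 25(1 − q). Pr(mE > mS) is 0.54 at q = 0, and 0.59, 0.64 and 0.74 at 5, 10 and 20%.

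**Would survival contact alone repair PFS?** Suppose progression goes unseen after withdrawal and the later death is counted instead. As an illustration, use the introduction's subgroup medians for sorafenib (TTP 4.1, OS 8.9 months) as the lag. The estimate is then 4.1 × [1 + q(8.9/4.1 − 1)], which is 4.58 at 10% and 5.06 at 20%. With the event lost altogether it is 4.56 and 5.1. For patients moved to other therapy, survival contact without scans recovers almost nothing. For ECOG 4 the lag to death should be much shorter, and survival contact should work well.

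**The case against.** Several points on the other side carry weight.

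- Withdrawal is optional, and no text says that withdrawn patients are censored. A reader might infer that PFS and OS will lose these patients; the documents support only that they can.
- A reader might also infer that withdrawal under 5.2 ends follow-up for death. The documents do not show this. Someone withdrawn from the study has also stopped treatment, so footnote h applies on its face, and deaths near the end-of-treatment visit must be reported. What remains for OS is that neither text says whether it covers subjects withdrawn under 5.2.
- The discretionary list mixes terms. Its pregnancy note speaks of withdrawal from study drug and cautions against contrast CT or MRI during pregnancy, which suggests that imaging could otherwise go on. This shows that the list is unclear; it does not settle the other reasons.
- The End of Treatment scan, if done, would record progression in some patients who go on to other therapy. ECOG 4 may also often come after progression has been counted. Both reduce the loss below the worst case.
- Section 6.3 says that if TheraSphere cannot be given "the patient will receive alternative or no treatment as previously defined in the treatment plan". A reader might infer that such patients automatically meet the withdrawal reason on off-protocol therapy. That does not follow: the protocol itself foresees the alternative, and Section 5.1.3 bars concurrent therapy.

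None of this supplies a PFS rule for a patient withdrawn without documented progression.

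**Conclusion.** The gap is real for the primary endpoint and should be closed. As written, Sections 5.2 and 8.1 together permit informative censoring of PFS in the combination's favour, and no other section rules it out. The computed sizes are an upper range: they rest on exponential times, on loss exactly at the event, and on assumed shares of 5 to 20%. Within that range the effect matters. Four lost events in 40 patients would lower the chance of stopping at a true 3 months from 0.53 to 0.33. The documents do not show that any such loss will occur or how often. For OS the finding is limited to an unresolved question between Section 5.2 and footnote h.

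**What to change.** 1. In Section 5.2, leave the listed clinical reasons as they stand. State that the discretionary reasons end study treatment only, and that follow-up ends only with withdrawal of consent to follow-up, true loss to follow-up, or death.
2. State that footnote h survival contact applies to all these subjects, and that the tumour assessments already scheduled in Table 7 continue until progression where the patient's condition allows.
3. In Section 8.1, state that deaths count as PFS and OS events. Record the start date of any other anticancer therapy and report PFS both with and without censoring at that date. Add a sensitivity analysis that counts withdrawal for clinical deterioration as an event.
4. Reconcile the replacement text at the end of Section 5.2. It calls subjects who leave before Y-90 for reasons other than toxicity not evaluable and to be replaced, then says that withdrawn subjects are not replaced. Dropping early progressions or deaths on that basis would bias PFS in the same direction.

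Cost: some sentences in Sections 5.2 and 8.1, one CRF date, and a few extra contacts and scans. The three-monthly contact already exists. The downside is that PFS without censoring at new therapy mixes in some effect of that therapy; reporting both versions makes this visible.

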- Patients who have received Yttrium-90 microspheres are not eligible.
- Patients who have an ECOG PS ≤ 1
- Patients who are categorized under BCLC-C stage
- Cirrhotic status of Child-Pugh class A. Child-Pugh status should be calculated based on clinical findings and laboratory results during the screening period.
- The following laboratory parameters:
 - Platelet count $\geq 60 \times 10^9/L$
 - Hemoglobin ≥ 8.5 g/dL
 - Total bilirubin ≤ 2.5 mg/dl
 - Alanine transaminase (ALT) and AST ≤ 5 x upper limit of normal
 - Serum creatinine ≤ 1.5 x the upper limit of normal
- Prothrombin time (PT)-international normalized ratio (INR) ≤ 2.3 or PT ≤ 6 seconds above control.

Plan for statistical analysis	
The primary analysis is to evaluate the toxicity profile, and the secondary analysis to assess the overall survival and progression-free survival. The study will be monitored for toxicity. Being descriptive in nature, this trial will not focus on hypothesis testing. Descriptive statistics will be computed for all continuous and categorical variables of interest. All statistical analyses will be performed using SAS (version 9.3; SAS Institute, Inc., Cary, NC). For the primary analysis, all patients received treatment will be included the analysis for toxicity. Continuous parameters will be summarized using descriptive statistics, such as number of patients, mean, standard deviation, median and range. The toxicities will be summarized with frequency and 95% confidence interval (95% CI) by type, severity and their relationship to the treatment. Assuming a 30% of grade 3 or 4 treatment related toxicity rate, with 20 patients, the 95% CI will be (9.9%, 50.1%).
 
For the secondary analysis, the Kaplan-Meier method will be applied to estimate the probabilities of overall survival and progression-free survival as well as the median OS duration and PFS duration. The Log rank test will be used to compare the two time-to-event outcomes between patient subgroups.

--------------------------------------	---

Imaging Requirements

- Triple Phase CT – To determine liver volume measurement, identify hepatic vascular anatomy to determine TheraSphere dosimetry
 - Spiral CT abdomen/pelvis –performed with cuts of 10 mm or less in slice thickness contiguously in the axial plane to assess hepatic and extra-hepatic lesions according to the RECIST 1.1 criteria.

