7.4 Safety

All subjects who receive at least one dose of study treatment will be valid for the safety analysis.

All observations pertinent to the safety of the study treatment will be recorded and included in the final report.

Safety variables include the following: AEs, laboratory changes (complete blood counts, electrolytes, chemistry, and coagulation), changes in vital signs (blood pressure, heart rate, respiratory rate, and temperature) and ECG at the investigator's discretion .

All AEs whether considered drug-related or not, will be reported in with a diagnosis, start/stop dates, action taken, whether treatment was discontinued, any corrective measures

taken, outcome, and other possible causes. For all events, the relationship to treatment and the intensity of the event will be determined by the investigator.

This trial will use the NCI-CTCAE v4.0 criteria for assessment of toxicity and SAE reporting with regard to toxicity grade.

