5	0.017	39.7 (40, 40)

If the trial continues to maximum accrual of 40 patients and maintains sufficient follow-up to observe 25 events (PD/death) with a median PFS of 4.1 months, then a 95% credible interval for median PFS would extend from 2.76 to 6.08 months.

Toxicity Monitoring

In addition, toxicity will be monitored closely in all patients using the method of Thall et al (1995). The interim monitoring will be first conducted after the first 20 patients have been evaluated and then be repeated after each cohort of 5 patients. Denote the probability of toxicity by θ_E , where toxicity is defined as any non-hematological Grade 3 or greater complications attributable to the treatment. We assume $\theta_E \sim \text{beta}(0.6, 1.4)$. We will stop the

trial if at any point $\Pr(\theta_E > 0.30 \mid \text{data}) > 0.85$. That is, we will stop the trial if, at any time during the study, we determine that there is more than 85% chance that the toxicity rate is more than 30%. Stopping boundaries corresponding to this stopping rule are listed in table 9.

Table 9: Stopping boundaries for toxicity monitoring

Among These Number of Patients	Recommend Stopping if Toxicity Observed in n or more patients
20	9
25	11
30	12
35	14

Table 10: The operating characteristics for toxicity monitoring are summarized in the following table

True toxicity probability	Probability of early stop	Sample size percentiles (10, 25, 50, 75, 90)
0.1	0.0001	40 40 40 40 40
0.2	0.017	40 40 40 40 40
0.3	0.211	25 40 40 40 40
0.4	0.651	20 20 25 40 40
0.5	0.938	20 20 20 20 30

Multc Lean V2.1 and OneArmTTE Version 4.1.1 were used for the trial design.

Futility monitoring in CTC website

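### Section 5.2 ties toxicity evaluability before Y-90 to the reason for leaving, while Sections 7.4 and 8.1 and the synopsis use all treated patients; if 5.2 governs, a qualifying toxicity can be left out of the Table 9 count

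*Combined protocol and SAP*

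**What the plan says.** Section 5.2, on drop-outs: "A subject who discontinues study participation for reasons other than toxicity after receiving sorafenib but not the Y-90 procedure is inevaluable and will be replaced". It continues: "Subjects who are discontinued from the study early due to toxicities will be counted in the toxicity assessment". A few lines later the same section states: "No withdrawn subjects will be replaced".

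Three other places describe the set for toxicity differently:

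- Section 7.4: "All subjects who receive at least one dose of study treatment will be valid for the safety analysis".
- Synopsis, plan for statistical analysis: "all patients received treatment will be included the analysis for toxicity".
- Section 8.1, Toxicity Monitoring: "toxicity will be monitored closely in all patients".

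Section 8.1 also fixes the event and the timing. The event is narrow: "toxicity is defined as any non-hematological Grade 3 or greater complications attributable to the treatment". On timing: "The interim monitoring will be first conducted after the first 20 patients have been evaluated", with further looks after every 5 patients. The section does not say what makes a patient evaluated.

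**The concern.** Section 8.1 defines toxicity by what happened to the patient. Section 5.2 sorts patients who leave before Y-90 by why they left. The two tests differ for a patient who has a qualifying event on sorafenib alone and then leaves for another reason.

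The plan's own rules make such a patient possible. For most non-hematological Grade 3 events, Table 3 has sorafenib interrupted and resumed at a lower level, so the patient stays on study. Section 4 keeps the Y-90 timing despite dose reductions or interruptions. The patient can then withdraw consent (Section 5.2 allows this without a reason), be lost to follow-up, or be refused Y-90 because of uncorrectable lung shunting or gastrointestinal flow (Section 6.3).

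What is at stake is the only formal toxicity stopping rule in the trial. Its boundaries turn on single patients, so two analysts who each follow the protocol could reach opposite decisions on the same data. The final toxicity rate and the final posterior probability would also depend on the section followed.

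**Working it through.** **Inputs from Section 8.1.** Prior for the toxicity rate theta_E: beta(0.6, 1.4). Stop if Pr(theta_E > 0.30 | data) > 0.85. Looks at 20, 25, 30 and 35 patients, maximum 40.

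**Step 1: reproduce the plan.** With s events in n patients the posterior is beta(0.6 + s, 1.4 + n − s). The boundary is the smallest s whose posterior probability exceeds 0.85.

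| n | Boundary s (Table 9) | Pr at s | Pr at s − 1 |
|---|---|---|---|
| 20 | 9 | 0.906 | 0.807 |
| 25 | 11 | 0.918 | 0.838 |
| 30 | 12 | 0.863 | 0.764 |
| 35 | 14 | 0.883 | 0.801 |

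An exact binomial recursion over these looks gives early-stop probabilities of 0.0001, 0.017, 0.211, 0.651 and 0.938 at true rates of 0.1 to 0.5, as in Table 10. The arithmetic is right for whatever set is counted; the open question is who is in the set.

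**Step 2: one patient near the boundary.** Suppose 8 of 20 counted patients have a toxicity, and one or two further treated patients left before Y-90 for other reasons.

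| Set | s/n | Pr(theta_E > 0.30) | Against 0.85 |
|---|---|---|---|
| Section 5.2 | 8/20 | 0.807 | continue |
| All treated, one leaver with an event | 9/21 | 0.876 | stop |
| All treated, two leavers, one with an event | 9/22 | 0.842 | continue |
| All treated, two leavers, both with events | 10/22 | 0.924 | stop |

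Table 9 has no row for 21 or 22. The same reversal appears at a scheduled look: if the leaver with an event holds one of the first 20 places instead of an event-free patient, the count is 9/20 and the probability 0.906.

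**Step 3: effect on early stopping.** Let x be the share of treated patients excluded under Section 5.2 and q their toxicity rate. With a true rate of 0.30 in all treated patients, the counted rate is

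(0.30 − x·q) / (1 − x).

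For x = 0.15 and q = 0.50: (0.30 − 0.075)/0.85 = 0.265. For q = 0.10: (0.30 − 0.015)/0.85 = 0.335. The documents give neither x nor q, so both are assumed over a range. Each cell shows the counted rate, then the early-stop probability from the Step 1 recursion.

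| x | q = 0.10 | q = 0.30 | q = 0.50 |
|---|---|---|---|
| 5% | 0.311; 0.251 | 0.300; 0.211 | 0.289; 0.176 |
| 10% | 0.322; 0.298 | 0.300; 0.211 | 0.278; 0.140 |
| 15% | 0.335; 0.355 | 0.300; 0.211 | 0.265; 0.106 |

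At a true rate of 0.40, excluding 10% with a toxicity rate of 75% lowers the early-stop probability from 0.651 to 0.474.

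**The case against.** The strongest reply is that the plan already settles the matter. The stopping rule sits in Section 8.1, which says all patients; Section 7.4 and the synopsis agree; and Section 5.2 never mentions Table 9. Much of this stands. A reader might infer that Section 5.2 removes these events from the stopping rule. The documents do not support that; they show an unresolved conflict, and the event is lost only if Section 5.2 is taken to govern. The conflict remains, however. Section 5.2 follows its inevaluability rule with a sentence about the toxicity assessment, so the rule cannot safely be read as concerning PFS alone. Section 8.1 counts evaluated patients without defining them, which invites use of the Section 5.2 definition.

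Other limits also stand:

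- Only attributable non-hematological events of Grade 3 or greater enter the rule, and Section 7.4 has all safety observations recorded and reported. What is at risk is the place of the event in the count and the rate, not its reporting.
- A reader might infer that Section 5.2 makes the monitoring too lenient. That holds only if leavers have more toxicity than those kept. If they have less, the counted rate is too high; if the rates match, there is no bias.
- A reader might use the plan's 4.1-month median as a guide to how many leave. Under an exponential model it implies about 11% to 18% with a PFS event by weeks 3 to 5. That is not a leaving rate: progression is not among the withdrawal reasons listed in Section 5.2, and Section 7.2 schedules tumor assessments every 8 weeks after Y-90.
- The reversal in Step 2 needs a count just below the boundary. With two leavers and one event, the decision does not change.

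**Conclusion.** The concern holds as a conflict that has to be resolved before the rule is applied. Section 5.2 uses the reason for leaving, the other three places use treatment received, and a single qualifying patient can turn a continue into a stop (0.807 against 0.876). The average effect on early stopping cannot be fixed from the documents. At a true rate of 30% and an assumed 15% excluded, it runs from 0.106 to 0.355 around the stated 0.211 as leavers' toxicity rate goes from 50% to 10%. At 5% excluded it runs from 0.176 to 0.251. These figures assume that counted patients share one toxicity rate and that each look takes place at the planned number of counted patients. Tables 9 and 10 are correct as computed and need no change for this reason.

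**What to change.** Use one toxicity set throughout.

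1. State in Sections 5.2 and 8.1 that every patient who received at least one dose of study treatment counts, in both numerator and denominator, for the Table 9 monitoring, the final toxicity rate and Pr(theta_E > 0.30 | data), whatever the reason for leaving.
2. Limit the term inevaluable in Section 5.2 to endpoints other than toxicity, and name them.
3. Define an evaluated patient in Section 8.1 consistently with item 1.
4. Report the Y-90-treated subset as a sensitivity analysis.
5. Reconcile the two replacement statements in Section 5.2 in the same edit, since they affect how many patients are dosed.

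Do not count early leavers with events while dropping those without. That selects on the outcome and always raises the counted rate, to 0.30/(1 − x(1 − q)). At a true rate of 30% with 15% leaving, it gives 0.324, 0.335 or 0.347 for leavers' rates of 50%, 30% or 10%, and early stopping of 0.307, 0.355 or 0.407 against 0.211.

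The cost is a few sentences and no new data, because adverse events are already recorded from consent. The downside is small: patients who never received Y-90 enter the denominator and can dilute the rate for the full combination. The sensitivity analysis shows by how much.
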